7.3.3 MCC Expedited Reporting Guidelines for MCC IITs

Investigators within MCC will report SAEs directly to the MCC DSMC per the MCC DSMC SOP and the University of Kentucky IRB reporting policy.

Attribution	MCC Reportable AEs				
	Gr. 2 AE Expected	Gr. 3 AE Unexpected	Gr. 4 AE Expected	Gr. 4 AE Unexpected	Gr. 5 AE Expected or Unexpected
Unrelated Unlikely	Only for eye/visual changes	Not required	5 calendar days [#]	5 calendar days	24 hours*
Possible Probable Definite	Only for eye/visual changes	5 calendar days	5 calendar days [#]	5 calendar days	24 hours*
# If listed in protocol as Expected and Not Requiring expedited reporting, the adverse event does not need to be reported.					
* For participants enrolled and actively participating in the study or for SAEs occurring within 30 days of the last intervention, the SAE should be reported within 24 business hours of learning of the event.					

7.4 Expedited Reporting to Hospital Risk Management

Participating investigators will report to the UK Office of Risk Management any participant safety reports or sentinel events that require reporting according to institutional policy.

7.5 Routine Adverse Event Reporting

[figure not shown]
All AEs must be reported in routine study data submissions to the PI on the OnCore case report forms. AEs reported through expedited processes (e.g., reported to the IRB) must also be reported in routine study data submissions.

8. PHARMACEUTICAL INFORMATION

A list of the adverse events and potential risks associated with HCQ administered in this study is found in Section 7.1.

8.1 Hydroxychloroquine

Description: Hydroxychloroquine sulfate, USP is a colorless crystalline solid, soluble in water to at least 20 percent; chemically the drug is 2-[[4-[(7-Chloro-4-quinolyl) amino]pentyl] ethylamino] ethanol sulfate (1:1). Hydroxychloroquine sulfate, USP has the following structural formula:

Molecular Formula: C₁₈H₂₆ClN₃O.H₂SO₄ Molecular Weight of 433.95

Each tablet, for oral administration, contains 200 mg hydroxychloroquine sulfate, USP (equivalent to 155 mg base). In addition, each tablet contains the following Inactive Ingredients: colloidal silicon dioxide, dibasic calcium phosphate, hypromellose, macrogol/PEG 3350, magnesium stearate, polysorbate 80, pre-gelatinized starch, talc, and titanium dioxide.

Hydroxychloroquine sulfate tablets, USP are white, to off-white, capsule-shaped tablets, debossed with "HCQS" on one side and plain on the reverse side and are available in bottles of 10, 100, 500 and 1000.

NDC 63304-296-0	Bottles of 10
NDC 63304-296-01	Bottles of 100
NDC 63304-296-05	Bottles of 500
NDC 63304-296-10	Bottles of 1000

8.2 HCQ Storage Requirements:

- 8.2.1 Dispense in a tight, light-resistant container as defined in the USP/NF.
- 8.2.2 Store at 20° - 25°C (68° - 77°F) excursions permitted to 15° - 30°C (59° - 86°F) [See USP Controlled Room Temperature].
- 8.2.3 Store out of the reach of children.

8.3 HCQ Stability:

When stored as listed above and light-resistant containers, hydroxychloroquine is stable for 3 years from manufacture date.

8.4 Route of Administration for HCQ:

Hydroxychloroquine is taken orally twice a day, each dose to be taken with a meal or a glass of milk. If patients miss the dose, take it within 2 hours. Outside of this 2-hour window, just skip the dose and take the next dose at the regular scheduled time. See **Appendix C**.

8.5 HCQ Contraindications

Use of HCQ is contraindicated in:

- (1) presence of retinal or visual field changes attributable to any 4-aminoquinoline compound,
- (2) patients with known hypersensitivity to 4-aminoquinoline compounds, and
- (3) for long-term therapy in children.

8.6 HCQ Precautions: General

Antimalarial compounds should be used with caution in patients with hepatic disease or alcoholism or in conjunction with known hepatotoxic drugs. Periodic blood cell counts should be made if patients are given prolonged therapy. If any severe blood disorder appears which is not attributable to the disease under treatment, discontinuation of the drug should be considered. The drug should be administered with caution in patients having G-6-PD (glucose-6-phosphate dehydrogenase) deficiency.

8.7 HCQ Overdose: Symptoms of Overdose and Treatment for HCQ Overdose

Overdose with the 4-aminoquinolines is dangerous particularly in infants, as little as 1-2 grams having proved fatal.

8.7.1 Symptoms of HCQ Overdose:

The 4-aminoquinoline compounds are very rapidly and completely absorbed following ingestion and in accidental overdosage, toxic symptoms may occur within **30 minutes**. These consist of:

headache, drowsiness, visual disturbances, cardiovascular collapse, hypokalemia and convulsions, rhythm and conduction disorders, including QT prolongation, torsade de pointes, ventricular tachycardia and ventricular fibrillation, followed by sudden potentially fatal respiratory and cardiac arrest.

Immediate medical attention is required, as effects may appear shortly after overdose.

The ECG may reveal atrial standstill, nodal rhythm, prolonged intraventricular conduction time, and progressive bradycardia leading to ventricular fibrillation and/or arrest.

8.7.2 Treatment of HCQ Overdose:

Treatment is symptomatic and must be prompt with immediate evacuation of the stomach by emesis (at home, before transportation to the hospital), or gastric lavage until the stomach is completely emptied. If finely powdered activated charcoal is introduced by the stomach tube, after lavage and within 30 minutes after ingestion of the tablets, it may inhibit further intestinal absorption of the drug. To be effective, the dose of activated charcoal should be at least five times the estimated dose of ingested hydroxychloroquine. Convulsions, if present, should be controlled before attempting gastric lavage. If due to cerebral stimulation, cautious administration of an ultrashort-acting barbiturate may be tried but, if due to anoxia, convulsions should be corrected by oxygen administration, artificial respiration or, in shock with hypotension, by vasopressor therapy. Because of the importance of supporting respiration, tracheal intubation or tracheostomy, followed by gastric lavage, has also been advised. Exchange transfusions have been used to reduce the level of 4-aminoquinolines in the blood. Consideration should be given to administering diazepam parenterally since studies have reported it beneficial in reversing chloroquine cardiotoxicity. A patient who survives the acute phase and is asymptomatic should be closely observed for at least 6 hours. Fluids may be forced, and sufficient ammonium chloride may be administered for a few days to acidify the urine to help promote urinary excretion. If serious toxic symptoms occur from over dosage or sensitivity, it is suggested that ammonium chloride (8 g daily in divided doses for adults) three or four days a week be administered for several months after therapy has been stopped, as acidification of the urine increases renal excretion of the 4-aminoquinoline compounds by 20 to 90 percent. However, caution must be exercised in patients with impaired renal function and/or metabolic acidosis.

9. IMMUNOLOGICAL EFFECT OF HCQ

To assess the immunological effect of HCQ therapy in patients, we will analyze peripheral blood mononuclear cells (PBMCs) at days 0 and 30 of treatment, and also, Day 60 (+ 6-week study visit window) of treatment. PBMC and plasma separation and storage will be handled by the Biospecimen Procurement and Translational Pathology Shared Resource Facility, per their standard processes until samples are ready for analysis.

Changes in markers of immune function/activation will be determined by measuring the percentage and absolute number of activated, naïve, and memory T cell subsets within CD4 helper, CD8 cytotoxic, and Treg subsets using cell marker antibodies to: CD4, CD8, CD45RA, CD45RO, CD25, and Foxp3. Th1, Th2 and Th17 subsets will be identified in the CD4 T cell subset by intracellular staining for IFN- γ , IL-10 and IL-17 in ex vivo activated PBMCs. Markers for systemic inflammation (C-reactive protein, IFN-gamma and TNFa) will be quantified in plasma samples. As a lysomotropic compound, HCQ reduces pH in lysosomes which can promote antigen retention and can promote autophagy. The pH levels in intracellular vesicles will be evaluated by flow cytometry in CD4 and CD8 T cell subsets and in monocytes using Lysensor Yellow/Blue DND-160. Induction of autophagy will be monitored in CD4 and CD8 T cell subsets and in monocytes by evaluating expression levels of the autophagy marker, LC3B.

To assess PAR-4 levels we will analyze plasma (or serum) at Day 0, 2 weeks prior to surgery or initiation of radiation treatment (corresponds to roughly Day 14 of HCQ therapy); 30-, 60- and 90-days post-HCQ initiation; and at the 6-month and 12-month follow-up timepoints (that correspond to a standard of care clinic visit 6- and 12-months after cessation of HCQ therapy).

See Study Lab Manual for additional details – a draft of the lab manual is **Appendix E**

10. Study Calendar / Schedule of Activities

Baseline evaluations are to be conducted within 8 weeks prior to start of HCQ. Scans and ophthalmologic exam must be completed less than 8 weeks prior to the start of HCQ regimen. In the event the patient's condition is deteriorating, laboratory evaluations should be repeated more frequently, as clinically indicated and at the discretion of the treating physician. At PSA progression or symptomatic progression: PSA, history and physical/toxicity assessment, CT C/A/P and/or fluciclovine or PSMA PET scans to be performed at discretion of treating physician, per standard of care.

Study Calendar											
Procedures	Pre-study Screening	Enrollment/Baseline Visit 1, Day 0	Day 14 post-HCQ initiation	Day 30 post-HCQ initiation	Day 60 post-HCQ initiation	90 days post-HCQ initiation	6-months post-HCQ cessation	1 Year Post- HCQ cessation	2 Years Post-HCQ cessation	3 Years Post-HCQ cessation	Off-Study
HCQ Drug Dispensing		R		R	R	R					
Adverse Event Evaluation		R	R	R	R	R					
HCQ compliance (pill diary)				R	R	R					
PAR-4 blood sample ¹		R	R	R	R	R	R	R			
PBMCs blood collection ²		R		R	R						
Quality of Life ³		R				R	R	R			
Informed Consent	R										
Demographics	R										
Ophthalmologic Exam ⁴	R	← ----- S ** ----- →									
PSA (serum, one tube) ⁵	S	R		R		S	S	S			
Imaging ⁶											
Fluciclovine or PSMA PET or PET/CT scan ^{6a}	S**										
Bone scan ^{6a}	S**										
CT chest, abdomen, pelvis ^{6a}	S**										
MRI of pelvis ^{6b}	S *										
Assessment of Disease Progression ^{6c}							S * , **				
CBC w/ differential	S	*	*	S	S	S	**	**			
CMP **	S	*	*	S	S	S	**	**			
Concomitant Medications ⁷	S	S	S	S	S	S					
Medical History	S										
Height ⁸		S									
Physical Exam with vitals (including weight) and ECOG Performance status	S	**	S**	S	S	S	**	**			
Survival Status									R	R	R
Record date of ADT initiation ⁹											

Study Calendar											
Procedures	Pre-study Screening	Enrollment/Baseline Visit 1, Day 0	Day 14 post-HCQ initiation	Day 30 post-HCQ initiation	Day 60 post-HCQ initiation	90 days post-HCQ initiation	6-months post-HCQ cessation	1 Year Post- HCQ cessation	2 Years Post-HCQ cessation	3 Years Post-HCQ cessation	Off-Study

NOTES: * per standard of care ** at the discretion of the treating physician.
 
Legend: S = standard of care; R = research; PSA, prostate-specific antigen; PET, positron emission tomography scan; HCQ, hydroxychloroquine; PAR-4, prostate apoptosis response-4; PSMA, prostate-specific membrane antigen PET scan
 
1: Blood (1 tube) will be drawn at each of the 7 noted timepoints for PSA and PAR-4 levels; plasma is preferred (serum is acceptable). Timepoints may be +/- 72-hour window at Pre-study and Enrollment. For Day 14, Timepoints may be +/- 120-hour window. Timepoints may be +/- 28-day window at the 3-, 6- and 12-month f/u, coinciding with a clinic visit.
 
2: for collection of PBMCs (peripheral blood mononuclear cells): one tube per collection timepoint, slated for Day 0, Day 30 and Day 60. Day 0 and Day 30 timepoints have a +/- 14-day window. Day 60 has a +6 week window. This is explicated in greater detail in study lab manual.
 
3: QOL is assessed via EORTC QLQ-C30 + QLQ-PR25 at 4 timepoints 
 - at a clinic visit prior to initiation of HCQ - at a clinic visit; either the end of HCQ administration OR when HCQ is discontinued (if stop it early) - at 6-mos and 12-mos post-treatment. These final two QOL timepoints can be +/- 8 weeks, and conducted during a regularly scheduled, standard of care clinic visit. 
 
4: Requisite pre-study eye exam; Eye exam may be repeated during HCQ administration if vision complaints.
 
5: One tube of blood will be drawn at each of the 6 noted timepoints for serum PSA; this is standard of care for baseline and every 3 months (4 of the 6 draws), with two additional draws scheduled. Timepoints may be +/- 72-hour window at screening and enrollment.
 
6: Imaging at baseline, pre-study: Patients who have confirmed recurrent disease of the prostate are deemed ineligible for this trial. As such, all eligible patients will undergo standard of care imaging to identify metastases (initial evaluation of status/extent of recurrent disease), including: 6a: All eligible patients will undergo standard of care imaging to assess extent of metastatic disease at baseline; fluciclovine or PSMA PET scans are preferred; other scans (PET/CT scan, bone scan and/or CT of the chest, abdomen and pelvis) may be performed as needed at baseline to assess extent of metastatic disease, per standard of care. 6b: Additionally, eligible patients who have undergone radiation prior to study enrollment will have an MRI of pelvis (in addition to previously named imaging studies) to assess for recurrent local disease. Suspicious lesions of the prostate seen on MRI will be biopsied. 6c: Imaging on Study as work-up for disease progression: Once a patient is enrolled on-study, imaging to assess disease progression will proceed per standard of care, based on clinical indicators such as rising PSA and/or other clinical symptoms. Per RECIST 1.1, tumor re-evaluation scheduled every 6-8 weeks at the discretion of the treating physician based on clinical indicators. Notably, a rising PSA and/or other clinical symptoms could trigger a scan/imaging in an earlier timeframe.
 
7: Concomitant Medications will be assessed per standard of care at the discretion of the treating physician; during HCQ administration, Con Meds will be assessed with a particular focus on medications contraindicated for use with HCQ.
 
8: Height will be evaluated once while on-study. Height can either be assessed via the patient's medical record, and/or assessed directly (in conjunction with vital signs during a clinic visit)
 
9: ADT initiation: record date and reason for ADT initiation. Reasons for ADT initiation include: PSA/biochemical progression, Symptomatic Progression, Local Progression of baseline-detected lesions (either soft-tissue or bone lesions), or Appearance of new metastatic lesions.
											

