
 - Men ages 18 and older with recurrent prostate cancer following primary treatment of localized disease with either surgery or radiation - Recurrence defined as PSA ≥ 0.2 ng/dl following prostatectomy OR a PSA increase ≥ 2 above nadir following radiotherapy of primary tumor - ≤ 5 synchronous metastatic lesions on CT C/A/P and/or fluciclovine or prostate-specific membrane antigen scan - ECOG 0-2 	
 - Brain or CNS mets - Prior XRT/surgery to a metastatic site; orchectomy - Prior ADT for metastatic disease or as adjuvant therapy in past two years - Hx of fracture or spinal cord compression - Currently treated with abiraterone, enzalutamide, apalutamide, chemotherapy, immunotherapy or radioisotopes - Macular degeneration - Serum testosterone less than 50 ng/ml - Receipt of HCQ in the past 6 months

STUDY ENDPOINTS

Primary: 3-mos PAR-4 levels

Secondary:

Median Progression-Free Survival and 1-yr ADT-Free Survival up to 3 years
 HCQ Toxicity and Tolerability
 Quality of Life

Correlatives: PBMCs (days 0, 30, 60 of HCQ treatment), immune function and activation, systematic inflammation, and autophagy induction

TABLE OF CONTENTS	Pages
Title Page / Protocol History & Summary of Changes	1 / 3
SCHEMA	4
Table of Contents	5-6

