5. TREATMENT PLAN

5.1 Enrollment and Screening Process

Prior to any study-required tests, subjects must first provide written informed consent to participate in this study.

All lab tests, ophthalmologic exam and radiographic studies should be completed within eight weeks prior to initiation of HCQ treatment.

Complete history, physical examination, and evaluation of performance status will also be performed during this 8-week timeframe.

Required lab work will include:

complete blood count (CBC); serum chemistry tests to include alkaline phosphatase, glucose, creatinine, electrolytes, AST (SGOT), total testosterone, and total bilirubin.

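### The PAR-4 sampling windows in the Study Calendar do not match the primary endpoint: the baseline draw has no pre-dose limit, and the 3-month draw may fall up to 28 days after Day 90

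*Combined protocol and SAP*

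**What the plan says.** **Baseline draw.** The Study Calendar (Section 10) schedules seven PAR-4 draws. The screening cell is empty, so the only pre-treatment draw is in the column headed "Enrollment/Baseline Visit 1, Day 0". HCQ is first dispensed in the same column, and the next columns are counted from HCQ initiation. Section 9 schedules the immune-cell samples "at days 0 and 30 of treatment", which treats Day 0 as a treatment day. Footnote 1 sets the window for the PAR-4 draw: "Timepoints may be +/- 72-hour window at Pre-study and Enrollment". It does not mention the first dose.

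Other text points to a pre-dose baseline. Section 10 opens with "Baseline evaluations are to be conducted within 8 weeks prior to start of HCQ", and Section 5.1 says "All lab tests, ophthalmologic exam and radiographic studies should be completed within eight weeks prior to initiation of HCQ treatment". Neither sentence names PAR-4, and it is not in Section 5.1's list of required laboratory work. Footnote 3 does set such a limit for the quality-of-life baseline: "at a clinic visit prior to initiation of HCQ".

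**3-month draw.** Footnote 1 continues: "Timepoints may be +/- 28-day window at the 3-, 6- and 12-month f/u, coinciding with a clinic visit". Section 11.1 lists a Day 90 draw, and the calendar has a column at 90 days after HCQ initiation.

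**Endpoint.** Sections 1.1, 2.6, 11.1, 13.1.1 and 13.3.1 all define success as a 50% rise from baseline within the HCQ administration or therapy period, given as three months or 90 days. Section 13.3.1 has no rule for a 3-month draw taken after that period.

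**The concern.** The baseline value is the denominator of every patient's percent change. If HCQ raises PAR-4 early, a baseline drawn after dosing has begun is too high and a true responder can be scored as a non-responder. A missed pre-dose sample cannot be recovered later.

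The 3-month draw is the last one that can count. If it is taken after treatment has ended, the analyst must either leave it out, and lose the patient's last value in the period, or let an off-treatment value into an endpoint defined as on-treatment. The plan does not say which. The primary result is a single proportion in about 18 patients, also examined at an interim look (Section 13.2) that informs whether accrual continues, so the choice should not be made after data are seen.

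**Working it through.** **1. The plan's own figure.** Inputs from Section 13.1.2: n = 18, null 0.20, alternative 0.50, two-sided 5%, stated power 84%.
- Null standard error: √(0.2 × 0.8/18) = 0.0943. Alternative standard error: √(0.5 × 0.5/18) = 0.1179.
- Power: Φ((0.30 − 1.96 × 0.0943)/0.1179) = 0.836. The stated 84% is reproduced by the normal approximation.

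**2. Windows (footnote 1).**
- Baseline: Day 0 ± 72 h is Day −3 to Day +3. If dosing starts on Day 0, the upper half lies after the first dose.
- 3-month draw: 90 − 28 = 62 and 90 + 28 = 118, which is 57 days inclusive. Days 91 to 118 are 28 days, and 28/57 = 49%.

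**3. What one patient is worth (n = 18, null 0.20).**

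| Responders | Exact two-sided p | Normal approximation |
|---|---|---|
| 6/18 | – | z = 1.414, p = 0.157 |
| 7/18 | 0.0513 + 0.0180 = 0.069 | z = 2.003, p = 0.045 |
| 8/18 | 0.016 | – |

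At 7/18 the exact p adds the lower-tail outcome of 0 responders (0.8^18 = 0.0180), which is less likely than 7 responders (0.0350). At 8/18 that outcome is more likely than 8 responders (0.0120), so only the upper tail counts. Under either test, moving one patient across the cut-off changes the result. Section 13.3.1 does not say which version will be used.

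**4. Post-dose baseline: illustration only.** The documents give no early PAR-4 kinetics. If PAR-4 has already risen by a fraction e at the baseline draw, the true rise needed to score is 1.5(1 + e) − 1. For e = 5%, 10% and 20% (assumed) this is 57.5%, 65% and 80%. Assume also a median true rise of 50% with a between-patient log-SD of 0.4. The response rate among late baselines is then 1 − Φ(ln(1 + e)/0.4) = 45%, 41% and 32%. If 10% of baselines are late (assumed), the overall rate is 0.9 × 0.5 plus 0.1 times that rate, or 49.5%, 49.1% and 48.2%. The effect is small if late baselines are few.

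**5. Keeping the wide window and discarding late draws: illustration only.** Suppose a fraction q of responders first reach +50% at the 3-month draw, and that draws spread evenly over Days 62 to 118 (both assumed). Dropping draws after Day 90 gives a response rate of 0.5 × (1 − q × 28/57).

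| q | Response rate | P(≥ 8/18) |
|---|---|---|
| none discarded | 0.500 | 76% |
| 10% | 0.475 | 69% |
| 20% | 0.451 | 61% |
| 30% | 0.426 | 53% |

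A rule that only excludes late draws could therefore cost more than the problem it solves. The window itself needs shortening.

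**The case against.** **Baseline.** The strongest reply is that the plan already places baseline work before HCQ. The opening of Section 10 says so, Section 11.1 lists this draw apart from those counted from HCQ initiation, and the 72 hours attach to enrollment rather than to the first dose. The window looks generic: footnote 5 repeats it for PSA, and footnote 1 names a pre-study visit that has no PAR-4 draw. Section 5.3 ties the start of HCQ to surgery or radiation, and Section 11.4.1 allows for HCQ starting after enrollment, in which case the window may be harmless. Much of this stands. A reader might infer that baselines will be drawn on drug; the documents support only an unreconciled conflict. What remains is that the general sentences do not name PAR-4 and the PAR-4 footnote lacks the limit written for quality of life.

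**3-month draw.** A reader might infer that any draw after Day 90 is off treatment. That does not follow. Section 5.5 allows for delays due to adverse events, and the calendar shows dispensing in the 90-day column. The arithmetic also depends on the footnote's 3-month visit being the Day 90 draw. That is the natural reading, as it is the only 3-month PAR-4 draw, but it is not stated.

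**Scoring rule.** A reader might also see a contradiction between the schema, which names 3-month PAR-4 levels, and the body. Five sections consistently say within the period; the schema entry is an abbreviation that needs aligning, not a competing rule.

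**Size.** Any test with 18 patients can turn on one of them, so that fact shows sensitivity, not bias. This is correct.

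**Conclusion.** The point holds as a mismatch between sampling windows and endpoint that is cheap to correct. Followed as written, footnote 1 permits a baseline draw up to 72 hours after the visit where HCQ is first dispensed. If the 3-month visit is the Day 90 draw, it also permits a draw as late as Day 118, with 49% of the window after Day 90. The first conflicts with Section 10's own opening; the second does not fit an endpoint confined to the HCQ period.

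The direction of the baseline error (hiding responders) depends on HCQ raising PAR-4 within days. The size of any bias cannot be computed from the documents; the figures in steps 4 and 5 of the working rest on assumed values. Nothing here challenges the 0.20 null, the 0.50 alternative or the sample size. Confidence is high in the window arithmetic and moderate in the practical effect.

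**What to change.** 1. **Footnote 1, baseline.** Set the PAR-4 window to run from 72 hours before Day 0 to before the first HCQ dose.
2. **Footnote 1, 3-month draw.** State that this is the Day 90 draw. Shorten the upper side so that the draw is taken by the end of the HCQ course (Day 90, or later where dosing was delayed) plus a few days' visit allowance. The lower side can stay.
3. **Section 13.3.1.** State that a PAR-4 draw outside its window does not count toward the primary proportion but stays in the profile analyses, and add a sensitivity analysis that includes it. Keep the existing rule that a rise at any countable draw within the period is a response. Settle this before the interim look.
4. **Schema.** Align the primary endpoint label with that rule.

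Do not add a cut-off at each patient's last dose. Evaluability requires 80% of the planned course (0.80 × 90 = 72 days), so a patient who stops near Day 72 is evaluable. Such a cut-off would drop his on-schedule Day 90 draw and narrow the endpoint below the 3-month or 90-day period in the text.

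The cost is slightly tighter scheduling of two draws and an occasional late draw that does not count. No draws are added, and the planned 0.50, 0.20 and sample size are unchanged.

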1.2 Secondary Objectives

- Median Progression-Free Survival (time to clinical progression)
- 1- and 3-year Androgen Deprivation Therapy (ADT) Free Survival
- HCQ Treatment toxicity (AEs and SAEs during HCQ administration) and radiation toxicity to be assessed and recorded utilizing the CTCAE v5.0. Surgical Complications will be scored using the Clavien-Dindo Classification (Appendix F).
- Immunological effect of HCQ by analyzing peripheral blood mononuclear cells (PBMCs) at day 0 and Day 30 of treatment, and also, Day 60 (+ 6 weeks) of treatment.
- Quality of life as measured by the EORTC QLQ-C30 + QLQ-PR25

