5.3 HCQ Administration

Hydroxychloroquine will be administered daily on an outpatient basis beginning 2 weeks before metastasectomy or initiation of radiation treatment to metastatic lesions. HCQ administration will be held the day of surgery for those patients undergoing surgical resection of their metastatic site(s) and will resume on post-operative day 1, and the missed dose will not be made up. Hydroxychloroquine will be administered orally at a total daily dose of 400 mg (200 mg BID) for 90-days. Tablets of HCQ are available in 200 mg strength.

Instructions on taking HCQ (patient version) are located in **Appendix C**.

To minimize nausea, HCQ is recommended to be administered in divided doses (one 200-mg tablet twice per day). The divided doses should be taken with meals, once in the morning and once at night. Should a subject have emesis and regurgitate the HCQ within 30 minutes of taking it, the dose may be repeated once, but if vomiting occurs longer than 30 minutes after ingestion, the dose should not be repeated.

Study participants will be required to keep a medication diary and to present the completed diary at the end of the treatment (**Appendix D**). Additionally, at the PI's discretion, study staff will call the participants periodically on an as-needed basis to monitor ongoing completion of the pill diaries while patient is on-study, e.g., if a patient misses a clinic visit.

Appropriate dose modifications are described in Section 6.

Adverse events and potential risks are described in Section 7.

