5.5 Duration of Therapy

In the absence of treatment delays due to adverse event(s), hydroxychloroquine treatment will continue for 3 months or until one of the following criteria applies:

- Disease Progression, assessed by standard of care and defined as either:
 - PSA progression (an increase in PSA > 25% above baseline at study entry), or
 - Symptomatic progression (increasing pain from metastatic lesion), or
 - Progression of baseline-detected lesions (soft-tissue lesions as assessed by RECIST and bone lesions as assessed by the MDA criteria (respectively, Appendix H.1 and Appendix H.2)).
Additionally, CT C/A/P and/or fluciclovine or PSMA PET scans may be performed at the time of either Symptomatic or PSA Progression at discretion of the treating physician.
 - Appearance of new metastatic lesions
- Intercurrent illness that prevents further administration of treatment
- Unacceptable adverse event(s)
- Patient decides to withdraw from the study
- General or specific changes in the patient's condition that render the patient unacceptable for further treatment in the judgment of the investigator

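### The PBMC sampling windows allow a baseline drawn up to 14 days after HCQ starts and a Day 60 sample drawn after it ends, which can bias the immune-marker change

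*Combined protocol and SAP*

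**What the plan says.** Section 1.2 lists the immunological effect of HCQ as a secondary objective, using PBMCs "at day 0 and Day 30 of treatment, and also, Day 60 (+ 6 weeks) of treatment". Section 9 repeats the schedule: "at days 0 and 30 of treatment, and also, Day 60 (+ 6-week study visit window) of treatment". The schema lists the same samples under correlatives.

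Note 2 of the Study Calendar (Section 10) sets the windows: "Day 0 and Day 30 timepoints have a +/- 14-day window. Day 60 has a +6 week window". It refers to the study lab manual for more detail. The draft manual in Appendix E names days 0, 30 and 60 but gives no windows and does not ask for a pre-dose draw.

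The opening text of Section 10 points the other way for baseline: "Baseline evaluations are to be conducted within 8 weeks prior to start of HCQ". It does not name PBMCs.

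On treatment, Section 5.3 states: "Hydroxychloroquine will be administered orally at a total daily dose of 400 mg (200 mg BID) for 90-days", "beginning 2 weeks before metastasectomy or initiation of radiation treatment to metastatic lesions". Section 5.5 qualifies the duration: "In the absence of treatment delays due to adverse event(s), hydroxychloroquine treatment will continue for 3 months", with earlier stopping for several listed reasons.

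Section 13 names no analysis for the PBMC markers and no rule for a sample drawn off schedule.

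**The concern.** Section 9 plans to study changes in immune markers. With a single arm, that means each patient's change from his own baseline. If the baseline is drawn after HCQ has begun, part of any effect is already in it and the difference is too small. A baseline near Day 14 also falls at about the time surgery or radiation starts. A sample labelled Day 60 of treatment but drawn after the last dose mixes on-drug and off-drug states.

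At stake is the reading of a secondary objective in about 20 patients, where a few mistimed samples carry weight. A real immune effect could be understated, or an off-drug value read as an on-drug one. The protocol shows elsewhere that it can write the needed rule: calendar note 3 ties the quality-of-life baseline to a visit before HCQ starts.

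**Working it through.** The plan gives no figure of its own on this point, so there is none to reproduce. The check is day arithmetic, followed by an illustration on stated assumptions.

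**Inputs**
- Windows: Day 0 and Day 30 at plus or minus 14 days; Day 60 at plus 6 weeks, or 42 days (Section 10, note 2).
- Day count: from the start of HCQ (Sections 1.2 and 9; calendar column titles).
- Planned course: 90 days (Section 5.3). The pill diary in Appendix D numbers dosing days 1 to 90, so Day 90 is taken as the last planned dosing day.
- Site-directed treatment: planned 2 weeks after HCQ starts, about Day 14 (Section 5.3).

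**Permitted draw days**
- Day 0 sample: 0 - 14 = Day -14 to 0 + 14 = Day 14. Days 1 to 14 are 14 of the 29 permitted days.
- Day 30 sample: 30 - 14 = Day 16 to 30 + 14 = Day 44.
- Day 60 sample: Day 60 to 60 + 42 = Day 102. That is 43 permitted days.

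**Consequences**
- Latest baseline: Day 14, on HCQ, at about the planned start of surgery or radiation.
- Shortest interval from baseline to the Day 30 sample: 16 - 14 = 2 days.
- Latest Day 60 draw after an uninterrupted course: 102 - 90 = 12 days after the last planned dose. Days 91 to 102 are 12/43 = 28% of the permitted days. If Day 0 is itself the first of the 90 dosing days, the last is Day 89 and the gap is 13 days.

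**Effect of late baselines (illustration)**

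Let f be the share of baselines drawn on HCQ and g the share of the effect already present at that draw. With a true mean change D, the same in all patients, and follow-up draws on time:

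observed mean change = (1 - f) x D + f x (1 - g) x D = D x (1 - f x g)

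The documents give neither f nor g. Both are assumptions:

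| f | g | Share of true change observed |
|---|---|---|
| 0.10 | 0.5 | 1 - 0.05 = 95% |
| 0.25 | 0.5 | 1 - 0.125 = 87.5% |
| 0.50 | 0.5 | 1 - 0.25 = 75% |
| 0.50 | 1 | 1 - 0.50 = 50% |
| 1 | 1 | 0% |

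No such range can be given for late Day 60 draws, because the documents do not say how fast immune effects fade after HCQ stops.

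**With a pre-dose Day 0 window**

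HCQ exposure at baseline falls from at most 14 days to none, and the shortest interval to the Day 30 sample rises from 2 days to 16 - 0 = 16 days.

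**The case against.** The strongest reply is that the baseline draw is meant to precede HCQ and note 2 is only loosely worded. The opening text of Section 10 says so in general terms. The first PBMC draw sits at the enrollment/baseline visit, where HCQ is first dispensed, and no PBMC draw is scheduled at the Day 14 visit. Shared visits for dispensing and sampling also favour draws near the nominal days. This makes late baselines less likely, but it does not remove the conflict: the general sentence does not name PBMCs, and the specific note permits 14 days after the start. The final lab manual might settle the matter, but only the draft is available, and it is silent.

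The off-drug part is conditional. Section 6 allows holds of up to 2 weeks, and Section 5.5 leaves room for delays to extend the course. If a 14-day hold did so, the last dose would fall on about Day 90 + 14 = Day 104, after the whole Day 60 window. Early stopping works in the other direction. A cap at a fixed Day 90 would therefore reject some on-drug samples. The 6 weeks also appears consistently in three places and looks deliberate. All of this stands.

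It also stands that site-directed treatment starts at about Day 14, so even punctual Day 30 and Day 60 draws normally follow it. Tighter windows will not separate an HCQ effect from that of surgery or radiation.

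A reader might infer that the immune comparison is certain to be corrupted, or that 14/29 or 28% of samples will be affected. The documents do not support this. Those fractions count permitted calendar days, not expected draws, and the windows allow mistiming without making it common. Nor does note 2 touch the primary endpoint: PAR-4 samples have their own windows in note 1, with plus or minus 72 hours at enrollment.

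**Conclusion.** The point holds as a conflict between two parts of Section 10 and as a gap in the analysis rules. Note 2 admits a baseline PBMC sample up to 14 days into HCQ, against the Section 10 statement on baseline evaluations. It also admits a Day 60 sample up to 12 days after a 90-day course, provided that dosing was not delayed. Nothing else in the documents corrects either.

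The result can bias the within-patient change in immune markers. On-HCQ baselines would usually shrink it, assuming that an early effect goes in the same direction as the later one and is no larger. The amount cannot be fixed without actual draw dates; under the assumptions shown, the observed change runs from 95% of the true change to none of it. The Day 60 part is the weaker of the two. The endpoint is secondary or correlative, so this calls for a modest correction and does not threaten the trial's main result.

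**What to change.** - Reconcile the opening text of Section 10 with note 2 by setting the Day 0 PBMC window to Day -14 up to before the first HCQ dose. Put the same rule in the lab manual.
- Keep the Day 60 visit window.
- Add to Section 13 a rule that classes each PBMC sample as pre-dose, on-HCQ or off-HCQ from its draw date and the pill diary. Define the boundary by the patient's actual last dose, not a fixed Day 90, and state in advance how a draw during a dosing hold is classed.
- Restrict the on-treatment comparison to pre-dose baselines and on-HCQ follow-up draws. Report off-HCQ draws separately.

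The classification also works for samples already collected. Appendix E plans to assay all cryopreserved samples in bulk after collection ends, so the rule can be fixed before results exist.

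The cost is an edit to the calendar, lab manual and Section 13, and a few samples lost from the main immune comparison.
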